8.3 Treatment Assessments

8.3.1 Baseline/Day 1 Visit

The following baseline tests and procedures must be completed prior to enrollment and dosing/dispensing:

- Confirm eligibility
- Assessment of AEs and concomitant medications
- Pregnancy Prevention Counseling
- Subject completes Quality of Life Surveys (FACT-F, PROMIS ED -Depression SF8a, SF36)
- Obtain urine samples (Reference Study Procedures Table Appendix 2)
- Pregnancy testing for women of childbearing potential only (Reference Study Procedures Table Appendix 2)
- Dispense 4 week study drug supply and backup bottle with MEMScaps™
- Instruct the subject on the packaging, storage and administration of the study drug

8.3.2 Weeks 2, 4, 6, 8, 10 (+/-3 days)

The following procedures/assessments are to be completed:

- Assessment of AEs and concomitant medications
- Obtain blood samples (Reference Study Procedures Table Appendix 2)
- Obtain urine samples (Reference Study Procedures Table Appendix 2)
- Pregnancy testing for women of childbearing potential only (Reference Study Procedures Table Appendix 2)
- Pregnancy Prevention Counseling
- Assess compliance with study drug dosing regimen including pill count
- Download MEMSCap™ Adherence Data
- Dispense study drug supply (weeks 4 and week 8, or as needed for emergency supply)
- Additionally, at week 4 visit only, subject will complete Quality of Life Surveys FACT-F, PROMIS ED -Depression SF8a, SF36)

8.3.3 End of Treatment (+/-3 days)

The following procedures/assessments are to be completed at the end of Epclusa treatment (Week 12):

- Assessment of AEs and concomitant medications
- Subject completes Quality of Life Surveys (FACT-F, PROMIS ED -Depression SF8a, SF36)
- Obtain urine samples (Reference Study Procedures Table Appendix 2)
- Pregnancy testing for women of childbearing potential only (Reference Study Procedures Table Appendix 2)
- Pregnancy Prevention Counseling
- Assess compliance with study drug dosing regimen including pill count
- Download MEMSCap™ Adherence Data

8.3.4 Early Termination Visit

The Sponsor-Investigator and other study staff (e.g., Medical Monitor, Sub-Investigator(s), and Clinical Project Manager) must be informed, as soon as possible, when a subject comes off treatment due to an AE.

If a subject discontinues treatment early for any reason then the following assessments for the Early Termination (ET) Visit must be performed:

- Assessment of AEs and concomitant medications
- Subject completes Quality of Life Surveys (FACT-F, PROMIS ED -Depression SF8a, SF36)
- Obtain blood samples (Reference Study Procedures Table Appendix 2)
- Obtain urine samples (Reference Study Procedures Table Appendix 2)
- Pregnancy testing for women of childbearing potential only (Reference Study Procedures Table Appendix 2)
- Pregnancy Prevention Counseling
- Assess compliance with study drug dosing regimen including pill count
- Download MEMSCap™ Adherence Data

8.4 Post-Treatment Assessments

All subjects must complete the Post-Treatment visits 4 and 12 weeks following the last dose of study drug.

8.4.1 Post-Treatment Week 4 and 12 (+/- 5 days)

The following procedures/assessments are to be completed:

- Assessment of AEs
- Pregnancy testing for women of childbearing potential only at the Post-Treatment Week 4 visit only (Reference Study Procedures Table Appendix 2)
- Obtain blood samples (Reference Study Procedures Table Appendix 2)
- Additionally, at post treatment week 12 visit only, subject will complete Quality of Life Surveys FACT-F, PROMIS ED -Depression SF8a, SF36)

Subjects with a HCV RNA > LLOQ at the Post-Treatment Week 12 Visit will return for confirmatory HCV RNA, preferably within 2 weeks.

8.5 Unscheduled Visit

A subject should attend an unscheduled visit if requested by the Sponsor-Investigator or Sub-Investigator(s). The assessments are at the requestor's discretion, and will at a minimum collect AE and concomitant medication information.

8.6 Assessments for Premature Discontinuation from Study Dosing

If a subject discontinues study drug dosing (for example, as a result of an AE), every attempt should be made to keep the subject in the study and continue to perform the required study-related follow-up and procedures. If this is not possible or acceptable to the subject or Sponsor-Investigator, the subject may be withdrawn from the study.

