5.4 HCV Virologic Response-Based Treatment Stopping Criteria

Treatment will be stopped if there is a less than 1 log₁₀ decline in HCV RNA after 4 weeks of therapy.

Confirmation should be performed as soon as possible and must occur no later than 2 weeks after an initial observation indicating virologic failure. All subjects who terminate treatment early will complete the Early Termination (ET) Visit, Week 4 and Week 12 Post-Treatment Visits.

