5.5 Treatment Discontinuation Criteria

The Medical Monitor should be consulted prior to subject discontinuation when medically feasible. Study drug must be discontinued in the following instances:

- Unacceptable toxicity, as defined in Section 9 of the protocol, or toxicity that, in the judgment of the Sponsor-Investigator or Sub-Investigator(s), compromises the ability to continue study-specific procedures or is considered to not be in the subject's best interest
- Pregnancy of female subject
- HCV efficacy failure as defined in Section 5.3
- Significant protocol violation
- Subject request to discontinue for any reason; it is important to determine and document whether the withdrawal of consent is primarily due to an adverse event (AE), lack of efficacy, or other reason
- Discontinuation of the study at the request of CRI, regulatory agency, or an Institutional Review Board (IRB)/Independent Ethics Committee (IEC)

If a subject meets discontinuation criteria during treatment, an Early Termination Visit will be required (Section 8.2.4). Early Termination Visits should be scheduled as soon as possible following discontinuation of treatment. Subjects that discontinue treatment early are still required to complete Post-Treatment Weeks 4, and 12 Visits.

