8.7.6 Location of Study Activities

This protocol is intended for study and implementation within the outpatient addiction clinic at Cambridge Health Alliance. The Community Research Initiative Sponsor-Investigator and study team will collaborate with the psychiatry team at the outpatient addiction clinic to implement the study and collect study data at the addiction clinic location on pre-specified days.

All procedures with study participants will take place at the outpatient addiction clinic and at a phlebotomy lab one flight downstairs from the addiction clinic. No study-related records or study drug will be stored at the outpatient addiction clinic. For each day session of study visits at the Sub-Investigator's clinic, study staff will transport documentation and study drug, on the day of the session, for only the subjects scheduled for visits that day. Study staff will bring blank source documentation worksheets, questionnaires, and informed consents as needed. Study staff will transport investigational drug securely to the clinic for the subjects scheduled, per CRI SOPs. Refer to section 7.4 for further detail on storage and transportation of study-related medication. Upon completion of source documentation worksheets, questionnaires, and ICFs, the study coordinator will immediately transport these study documents and returned study medication containers to the CRI office for secure storage.

To ensure maintenance of subject confidentiality, the following procedures with study records will be followed:

- Any documentation from the subject medical record that contains subject identifying information will be faxed from the clinic to Community Research Initiative via secure fax, for inclusion in the subject source document. These items will be certified copies of the original faxed documents.
- Informed consent documents must include patient names and signatures and in accordance with the regulations, must be original documents. These documents will be transported by the study coordinator directly from the clinic to Community Research Initiative for secure storage. They will be transported in a private vehicle (i.e. livery or privately owned automobile) in the direct possession of the study coordinator and in a securely locked carry-case.
- To maintain subject confidentiality, all other source documentation worksheets completed at study visits will not have patient names or identifying information. These documents will be

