10.3 Data Handling Conventions

Missing data can have an impact upon the interpretation of the trial data. Other than the endpoints discussed below, values for missing data will not be imputed.

For the analysis of post-baseline categorical efficacy endpoints, if a data point is missing and is preceded and followed in time by values that are deemed successes, then the missing data point will be termed a success; otherwise the data point will be termed a failure.

Any subject with missing data due to premature discontinuation of the study drug will be considered a failure at the date of premature discontinuation and all time points subsequent to the date of premature discontinuation if there are no observed values available. If no HCV RNA values are obtained after the last dose of study drug, the subject will be considered a treatment failure for the SVR endpoints.

Where appropriate, safety data for subjects that did not complete the study will be included in summary statistics.

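### Section 8.6 lets the Sponsor-Investigator end follow-up of a subject who stops drug, against 5.4, 5.5 and 8.4, and 10.3 then scores that subject an SVR12 failure

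*Combined protocol and SAP*

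**What the plan says.** Section 8.6 covers a subject who stops study drug. Its default is retention: "every attempt should be made to keep the subject in the study and continue to perform the required study-related follow-up and procedures". The next sentence is the exception: "If this is not possible or acceptable to the subject or Sponsor-Investigator, the subject may be withdrawn from the study". The section does not say what would make follow-up unacceptable to the Sponsor-Investigator, and it does not ask for the Week 12 HCV RNA to be sought first.

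Three other sections allow no exception:

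- 5.4: "All subjects who terminate treatment early will complete the Early Termination (ET) Visit, Week 4 and Week 12 Post-Treatment Visits".
- 5.5: "Subjects that discontinue treatment early are still required to complete Post-Treatment Weeks 4, and 12 Visits".
- 8.4: "All subjects must complete the Post-Treatment visits 4 and 12 weeks following the last dose of study drug".

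Section 9.6 also calls for both visits to be scheduled after a stop for toxicity.

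On scoring, 10.2.1.1 puts every enrolled subject with at least one dose in the efficacy set. Section 10.3 says of a subject with no HCV RNA after the last dose: "the subject will be considered a treatment failure for the SVR endpoints". On place, 8.7.6 says: "All procedures with study participants will take place at the outpatient addiction clinic and at a phlebotomy lab one flight downstairs".

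**The concern.** Stopping drug and leaving the study are different events. For SVR12, a subject who stops early can still be a success, provided the Week 12 sample is taken. Sections 5.4, 5.5 and 8.4 respect that distinction. Section 8.6 blurs it by letting one person's view of acceptability end follow-up.

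SVR12 is the primary endpoint and the measure named in the primary objective. The study is open label (7.1). Week 4 HCV RNA, urine drug screens, pill counts and MEMS data are all collected during treatment (7.4, Appendix 2), so a withdrawal decision can be made with that information at hand. If the subject would have cleared the virus, the recorded outcome depends on the decision and not on the virology. Withdrawal also loses that subject's Post-Treatment Week 12 quality-of-life surveys.

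**Working it through.** The plan gives no power calculation, target rate or sample-size derivation, so there is no stated figure to reproduce. The check has three parts.

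**1. How a withdrawn subject is scored**

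- The subject had at least one dose, so 10.2.1.1 keeps the subject in the denominator.
- Appendix 2 marks HCV RNA at screening, at Week 4 on treatment and at the post-treatment visits. The end-of-treatment/early-termination column has none. A subject withdrawn at the Early Termination visit would normally have no HCV RNA after the last dose, and 10.3 makes that a failure.
- If withdrawal comes after a Post-Treatment Week 4 value below LLOQ, the bracketing rule in 10.3 applies. A missing value is a success only when successes lie on both sides of it. No visit is scheduled after Post-Treatment Week 12, so a missing Week 12 value is again a failure.
- A subject who would have been above LLOQ at Week 12 is a failure either way. Withdrawal can therefore lower the SVR12 rate or leave it unchanged. It cannot raise it.

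**2. Size**

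Inputs: n = 20 (5.1, approximate); all other subjects respond (assumption); k would-be responders withdrawn (assumption). Section 10.5 asks for a 95% confidence interval but names no method. I assume Clopper-Pearson, with x = 20 − k: lower limit = Beta quantile 0.025 (x, n − x + 1); upper limit = Beta quantile 0.975 (x + 1, n − x), set to 1 when x = n.

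| k | x/n | SVR12 | Exact 95% CI |
|---|---|---|---|
| 0 | 20/20 | 100% | 83.2-100% |
| 1 | 19/20 | 95% | 75.1-99.9% |
| 2 | 18/20 | 90% | 68.3-98.8% |
| 3 | 17/20 | 85% | 62.1-96.8% |

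Each loss costs 1/20 = 5 points on the estimate. The lower limit falls by 83.2 − 75.1 = 8.1 points for the first loss, 75.1 − 68.3 = 6.8 for the second and 68.3 − 62.1 = 6.2 for the third. As a check on the choice of method, Wilson intervals are 83.9-100% for 20/20 and 76.4-99.1% for 19/20.

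**3. How often it could arise**

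The only related figure is in 3.2: 0.2% of subjects in the three Phase 3 trials discontinued for adverse events. Applied here, the expected number is 20 × 0.002 = 0.04, and the chance of at least one is 1 − 0.998^20 = 0.039, about 4%. This does not cover the other routes in 5.5, such as a significant protocol violation or the subject's own request, which the documents do not quantify. It also says nothing about how often the Sponsor-Investigator would then end follow-up.

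**The case against.** The strongest reply is that 8.6 already puts retention first, so withdrawal is a fallback. Any effect on SVR12 needs three things in the same subject: an early stop, withdrawal on the Sponsor-Investigator's side and not the subject's, and HCV RNA below LLOQ at Week 12 despite incomplete treatment. The primary analysis is a percentage with an interval and no threshold, so no formal decision turns on the bound. The objective concerns treatment delivered within addiction-clinic visits, and counting a subject lost from that setting as a failure is a defensible choice. Nothing suggests that drug screens would prompt withdrawal; 8.7.1.1 describes supportive responses. All of this stands and limits the size of the point. It does not remove the contradiction with 5.4, 5.5 and 8.4, or supply the missing criterion. A subject's own right to withdraw is not in question.

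A reader might go further in three ways that the documents do not support.

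- **That the direction of bias cannot be recovered.** It can: the subject stays in the denominator and is scored a failure. Section 11.5 also requires the reason for early discontinuation in the source data.
- **That someone who has left the programme has no permitted place for the sample.** Section 8.7.6 fixes the location but does not bar former patients from the clinic or its laboratory. It also lets medical-record documents be faxed in as source. What it lacks is any stated alternative for a subject who cannot attend, and any statement that an outside HCV RNA counts for the endpoint.
- **That SAEs after withdrawal are simply lost.** Section 9.3 keeps SAE reporting open to at least 30 days after the last dose and covers later events that the Investigator learns of and deems relevant to study drug. The planned safety summaries (10.2.1.2, 10.6) end at 30 days after the last dose.

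**Conclusion.** The point holds in a limited form. Section 8.6 contradicts 5.4, 5.5 and 8.4 by allowing withdrawal from follow-up at the Sponsor-Investigator's discretion without a criterion. Through 10.2.1.1 and 10.3, that decision fixes the subject's SVR12 value as failure whatever the virology. The bias is conservative and its direction is known, but it still understates effectiveness for a reason unrelated to treatment.

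One lost responder moves SVR12 from 100% (83.2-100%) to 95% (75.1-99.9%). This rests on 20 subjects, all others responding and a Clopper-Pearson interval. How many such losses will occur is an assumption; none is quite possible, and the documents give no basis for expecting two or more. The case for changing the text is that the missing data are avoidable and the change is cheap, not that the result is likely to be badly wrong.

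**What to change.** 1. In 8.6, delete the Sponsor-Investigator's acceptance as a ground for withdrawal, and separate stopping study drug from leaving the study. State that follow-up ends only for withdrawn consent, death, loss to follow-up or study termination (11.12), with the reason documented, and that the visits required by 5.4, 5.5 and 8.4 otherwise apply.
2. In 8.7.6, allow the Post-Treatment Week 4 and 12 HCV RNA to come from another accredited laboratory or the medical record when the subject cannot attend the clinic. Record the assay and its LLOQ and flag these results.
3. In 10.5, report SVR12 failures separately as virologic or missing. In the one-loss example this would show 19 responders, no virologic failure and one missing value, and a reader could see at once why the rate is 95%.

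The cost is a few sentences. The synopsis already treats laboratory assessments as standard of care. The one real downside is in item 2: the synopsis names a single HCV RNA test, and an outside result may come from a different assay with a different LLOQ, which is why it should be flagged.

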8.7 Procedures and Specifications

8.7.1 Clinical Laboratory Analytes

- Blood Collection
 - All required laboratory blood assessments will be conducted as described in Appendix 2, and per the discretion of the Sponsor-Investigator or Sub-Investigator(s). Additional assessments may be conducted per standard of care at the enrolling site and per the discretion of the Sponsor-Investigator or Sub-Investigator(s).

- Urine Collection
 - Urine assessments for drug screening and pregnancy (in WOCBP) will be conducted as described in Appendix 2. Additional assessments may be conducted per standard of care at the enrolling site and per the discretion of the Sponsor-Investigator or Sub-Investigator(s).

8.7.1.1 Management of Positive Urine Drug Screening Assessment

In the event that a study subject has a positive urine drug screen the subject will be managed according to the judgment of the Sub-Investigator. Interventions may include increased frequency of study visits, additional remote monitoring and support, and enhanced supplemental services for substance use prevention.

8.7.2 Medical History

Selected medical history will be collected by subject self-report and available medical records, including:

- risk factor for HCV
- estimated duration of HCV infection
- prior assessments of fibrosis
- HCV genotype if known
- prior HCV treatment
- comorbid liver diseases including hemochromatosis, autoimmune hepatitis, alpha-1-antitrypsin deficiency, obesity
- history of hepatic decompensation including variceal bleed, ascites, and encephalopathy
- clinically significant, active in the last year and ongoing conditions at time of enrollment

8.7.3 Quality of Life Surveys

- Quality of life surveys included in this study are Functional Assessment of Chronic Illness Therapy-Fatigue (FACIT-F), PROMIS Short Form v1.0 - ED-Depression 8a (PROMIS ED -Depression SF8a), Short Form Health Survey (SF36) which will be completed by subjects at Baseline/Day 1, on treatment week 4 visit, End of Treatment/Early Termination visits and post treatment week 12 visit. The subject should read and complete the surveys by himself/herself and write/mark answers directly onto the questionnaire.

8.7.4 Missed Visits

In the event that a subject misses a scheduled clinic visit, the study staff will telephone the subject within 24 hours of the missed visit. Another study visit will be scheduled for as soon as possible. The study staff will counsel subjects on how to continue study drug dosing from their back-up medication pack until the rescheduled visit, to ensure no missed doses.

8.7.5 Mentorship

Participating psychiatrists must consent to participate in the study. A consent form will be provided to the psychiatrist-buprenorphine/naloxone provider prior to the initial training session with ample time for the psychiatrists to read the consent and have their questions answered. They will be offered the opportunity to review the consent with study investigators by telephone or in face-to-face meetings with a study investigator or study team member. If they agree to consent, the signing of the consent will occur in the presence of a study team member, who will cosign the document. A copy of the signed consent will be provided to each psychiatrist-buprenorphine/naloxone prescriber. The original will be kept in a secure, locked study file at the CRI facility. Study consent procedures consistent with CRI SOP for informed consent will be followed (outlined in detail in section 8.1).

After consenting to participate, but prior to screening the first subject, the psychiatrists at the outpatient addiction clinic will undergo a training session with the Sponsor-Investigator which will address the management of HCV. The following topics will be addressed:

- Pathogenesis of HCV infection
- Goals of therapy/benefits of curing HCV
- Pre-treatment assessment, including diagnosis of cirrhosis
- Usage of Epclusa

The session will be based on the teaching slides in Appendix 6.

In addition, the Sponsor-Investigator will provide regularly scheduled weekly telephone support to the psychiatrists.

The psychiatrists' comfort level with providing care for patients with HCV infection will be determined by a questionnaire administered prior to the training session, after the training session, and after 4 months of actively treating subjects (Appendix 3). All responses to these questionnaires will be kept strictly confidential.

8.7.6 Location of Study Activities

This protocol is intended for study and implementation within the outpatient addiction clinic at Cambridge Health Alliance. The Community Research Initiative Sponsor-Investigator and study team will collaborate with the psychiatry team at the outpatient addiction clinic to implement the study and collect study data at the addiction clinic location on pre-specified days.

All procedures with study participants will take place at the outpatient addiction clinic and at a phlebotomy lab one flight downstairs from the addiction clinic. No study-related records or study drug will be stored at the outpatient addiction clinic. For each day session of study visits at the Sub-Investigator's clinic, study staff will transport documentation and study drug, on the day of the session, for only the subjects scheduled for visits that day. Study staff will bring blank source documentation worksheets, questionnaires, and informed consents as needed. Study staff will transport investigational drug securely to the clinic for the subjects scheduled, per CRI SOPs. Refer to section 7.4 for further detail on storage and transportation of study-related medication. Upon completion of source documentation worksheets, questionnaires, and ICFs, the study coordinator will immediately transport these study documents and returned study medication containers to the CRI office for secure storage.

To ensure maintenance of subject confidentiality, the following procedures with study records will be followed:

- Any documentation from the subject medical record that contains subject identifying information will be faxed from the clinic to Community Research Initiative via secure fax, for inclusion in the subject source document. These items will be certified copies of the original faxed documents.
- Informed consent documents must include patient names and signatures and in accordance with the regulations, must be original documents. These documents will be transported by the study coordinator directly from the clinic to Community Research Initiative for secure storage. They will be transported in a private vehicle (i.e. livery or privately owned automobile) in the direct possession of the study coordinator and in a securely locked carry-case.
- To maintain subject confidentiality, all other source documentation worksheets completed at study visits will not have patient names or identifying information. These documents will be

completed utilizing the unique 3 letter code and study specific numeric code number assigned upon screening and enrollment.

Community Research Initiative will maintain and store all essential documents and study medication for this study. All study data entry into the eCRF will occur at the CRI office by trained study staff. Ongoing regulatory filing, maintenance of essential documents and monitoring of study data will occur at the CRI office and be conducted by trained study staff.

